- 5. Refer to Section 7.1 and 7.2 for the follow-up requirement for subjects who discontinue from IMP or withdraw from the study.
- Height at Screening Visit 1 only.
- 7. IMP will be administered Q2W after collecting all testing/examination data at each visit (refer to #20 for additional vital signs at Visit 3). Subjects will be monitored for 1 hour at the site after dosing.
- Urine drug screen includes amphetamine, barbiturates (except for sites in China), benzodiazepines, tetrahydrocannabinol, cocaine, methadone, methamphetamine, opiates, phencyclidine, and tricyclic antidepressants (except for sites in China).
- 9. Serum pregnancy test at Visit 1 only, and urine pregnancy test at Visits 3, 5, 7, 9 and 10. Negative result must be obtained prior to randomization at Visit 3.
- 10. Mammogram for females aged 40 and over only (can be performed at any time during screening period), unless mammography or MRI were performed with normal results within 12 months prior to randomization.

Version 6.0 16 of 138 April 11,2024

- 11. Cervical cytology can be assessed at any time during the Screening period. (Virgins may be exempted per the investigator's discretion)
- 12. DXA scan and Sellar MRI can be assessed at any time during the Screening period. Only subjects who have greater chances of enrollment into the study will undergo DXA scan and Sellar MRI. For subjects who are eligible for randomization, the Screening DXA data will be used as baseline.
- 13. Subjects who discontinue from IMP prior to week 11 or become pregnant during the study does not require a DXA scan. For more details, including subjects who needs further DXA scan after EOT visit, refer to Section 8.2.7.
- 14. TVU should be performed during the early proliferative phase of the subject's menstrual cycle (approximately days 4 through 8). In some circumstances, transrectal or transabdominal ultrasound is allowed per the investigator's discretion.
- 15. Viral serology tests include anti-HAV, HBsAg, HBcAb, anti-HCV, HCV RNA (for positive or equivocal anti-HCV), and HIV antigen/anti-HIV (1+2).
- 16. Clinical laboratory tests are listed in Section 10.2. Samples of sex hormones (PRL, LH, FSH, estradiol, progesterone, testosterone, DHEAS) will be collected at the menses cycle days 1 to 5, and subjects should not take any opioids 2 days prior to blood sampling of PRL.

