5.1 Inclusion Criteria

Subjects are eligible to be included in the study only if all of the following criteria apply:

- 1. Pre-menopausal female subjects, between 18 and 49 years of age, inclusive, at the time of signing informed consent.
- 2. Subject must have a clinical diagnosis of endometriosis (laparoscopy or laparotomy) as documented by medical records within 10 years before screening.
- 3. Subject must have a Composite Pelvic Signs and Symptoms Score (CPSSS, refer to Section 8.11 and 10.9) total score of ≥ 6 at screening with a score of at least 2 for DYS and at least 2 for NMPP.
- 4. Subject must have reported at Baseline at least 2 days of "moderate" or "severe" pain for DYS and NMPP, with NRS score of at least 4 (where 0 represents absence of pain and 10 indicates unbearable pain, refer to Section 8.1.3 and 10.6).
- 5. Mammography or contrast-enhanced breast MRI performed within the last 12 months prior to randomization without clinically significant abnormal findings in subjects aged 40 and over only (subject with BI-RADS Classification 1 3 is eligible for randomization).
- 6. Subject must have at least two consecutive regular menstrual cycle (i.e. 21 to 35 days in duration) prior to Day 1.
- 7. Subject agrees to use required (nonhormonal) birth control methods during the entire length of participation in the study (refer to Section 10.4) and agrees to avoid pregnancy from signing the informed consent until 3 months after the last dose.
- 8. Subject must agree to use only those rescue analgesics (i.e. not prophylaxis) permitted by the protocol during the Screening, Treatment and Posttreatment follow-up Periods for her endometriosis-associated pain. (refer to Section 6.5.1).

Version 6.0 33 of 138 April 11, 2024

- 9. In the Investigator's opinion, subject is able to understand the nature of the study and any risk involved in participation in this study and is willing to cooperate and comply with the protocol restrictions and requirements, including transvaginal ultrasound (TVU).
- 10. Subject agrees not to participate in another interventional study while participating in the present study.
- 11. Subject who is willing to limit alcohol consumption during the study to no more than approximately one alcoholic drink or equivalent [beer (354 mL/12 ounces), wine (118 mL/4 ounces), or distilled spirits (29.5 mL/1 ounce)] per day.

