10.4 Appendix 4: Contraceptive Guidance

Woman of Childbearing Potential (WOCBP)

A woman is considered fertile following menarche and until becoming post-menopausal, unless permanently sterile. All subjects in this study are WOCBP and must follow the contraception requirements below. This includes women with tubal infertility from endometriosis.

Exception: Women who have had a documented bilateral salpingectomy or bilateral tubal ligation may participate in the study, but do not have to follow protocol-specified contraception requirements.

Note: Documentation of bilateral salpingectomy can come from the site personnel's review of the subject's medical records, medical examination, or medical history interview.

Contraception Requirements

A woman is eligible to participate in the study if she meets one of the following criteria:

• Is heterosexually abstinent;

Note: Sexual abstinence is defined as refraining from heterosexual intercourse during the entire period of risk associated with the study intervention. The reliability of sexual abstinence needs to be evaluated in relation to the duration of the study and the preferred and usual lifestyle of the subject.

OR

- Is heterosexually active and agrees to use two forms of the following contraception methods consistently and correctly during the protocol-defined time frame in inclusion and exclusion criteria:
 - Condoms used with spermicide (cream, spray, foam, gel, suppository, or polymer film)
 or Phexxi
 - o Diaphragm used with spermicide (condom may or may not be used) or Phexxi
 - o Cervical cap used with spermicide (condom may or may not be used) or Phexxi
 - o Vaginal sponge impregnated with spermicide or Phexxi; used with a condom

Note: Hormonal contraception except for sporadic use of emergency contraception is not permitted during the study. Male and female condoms should not be used at the same time. **OR**

• Has undergone bilateral tubal sterilization or bilateral salpingectomy;

OR

• Has a vasectomized partner.

Note: Partner must be the sole male sexual partner of the WOCBP and the absence of sperm has been confirmed. If not, a two-forms method of contraception must be used.

Subjects should avoid pregnancy from signing the consent until the completion of the study or 3 months after the last dose of IMP, whichever is longer.

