7.2.5 Other Analyses

Percentage Change from Baseline

The percentage change of DYS measured by NRS from Baseline to Week 12 will be performed the same method as analysis of primary outcome in section 7.2.2.

Percentage change from Baseline = (the mean of Visit - the mean of Baseline) / the mean of Baseline)*100%.

The Visit refers to Week 12 measurement or other post-baseline visits.

E-diary Compliance

All subjects will be administered an e-Diary after adequate training at Visit 2. Subjects are required to record uterine bleeding and endometriosis-associated pain every day for the entire duration of the study (until end of study). The use of rescue medications for endometriosis-associated pain will also be recorded. Compliance to e-Diary filling will be summarized for treatment group using PAS including the following variables:

Planned e-Diary Duration (days) = Date of Last Study Visit – Date of Visit 2 +1.

If a subject completed or discontinued the study early, the date of last study visit will be the day of EOS. If a subject is still ongoing, the date of last visit will be replaced by the date of last e-Diary record or last visit date (if applicable), whichever comes last.

- Total days with e-Diary (days) is the total days during study with e-Diary data. All days with non-missing e-Diary regardless of correction or refilling will be included.
- Compliance to e-Diary (%) = (Total Days with e-Diary / Planned e-Diary Duration) × 100.

Based on above calculation formula of e-Diary compliance, another compliance (%) will be calculated to exclude those days with missing and corrected/refilled e-Diary from today days with e-Diary (days).

E-diary data will be listed on the PAS.

Receiver Operating Curve (ROC) Analysis for Determination of Thresholds for Reduction in Pain

The ROC analysis will contain all subjects who received at least one dose of IMP.

- Subjects who a) prematurely discontinue before Week 13, or b) either prematurely discontinue at or after Week 13 but are missing Week 13 PGIC will be assigned a PGIC response of "No change" (PGIC Non-responder).
- Observed values of DYS measured by NRS without any imputation will be used for ROC analysis.

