7.3 Secondary Efficacy Endpoint

[figure not shown]
The analysis methods for the secondary endpoints are summarized in the table below.

Secondary Endpoints	Analysis Methods	Missing Data Handling
Change of NMPP measured by NRS from Baseline to Week 12 and 24	Following same steps in Section 7.2.2 for the primary endpoint	
	ANCOVA (as used for the primary endpoint)	MI approach (as used for the primary endpoint)
CFB in the monthly mean Endometriosis Daily Impact Pain Scale for DYS, NMPP and DYSP at Week 12 and 24	Following same steps in Section 7.2.2 for the primary endpoint	
	ANCOVA (as used for the primary endpoint)	MI approach (as used for the primary endpoint)
Change of DYS measured by NRS from Baseline to Week 24	Following same steps in Section 7.2.2 for the primary endpoint	
	ANCOVA (as used for the primary endpoint)	MI approach (as used for the primary endpoint)
Change of DYSP measured NRS from Baseline to Week 12 and 24	Following same steps in Section 7.2.2 for the primary endpoint	
	ANCOVA (as used for the primary endpoint)	MI approach (as used for the primary endpoint)
CFB by visit in permitted rescue medication use	The number of medication and the percentage of days that permitted rescue medication is used will be summarized as two separate endpoints	Missing data will not be imputed
	Analysis of variance (ANOVA)	
Change in menstrual period heaviness (bleeding) from Baseline by visit	The changes of mean scores of heaviness (bleeding) in the menstrual cycle collected from eCOA.	Missing data will not be imputed

[figure not shown]
7.3.1 CFB in DYS Measured by NRS at Week 24

The Measurement of Week 24: because the Week 24 (EOS) visit may or may not occur during menstruation, the measurement of Week 24 will be defined by the following 2 approaches, depending on the scenarios. The objective of these approaches is to capture a complete menstrual cycle and designate it as the EOS menstrual cycle.

- If EOS visit occurs during menstruation, the EOS menstrual cycle is defined as the interval that begins from the first day of the previous menstruation to the day before the first day of the menstruation during which the EOS visit occurred.

- If EOS visit occurs outside of a menstruation period, the latest menstruation period prior to the EOS visit will be identified. The EOS menstrual cycle will begin at the end of the menstruation period immediately before the latest menstruation period to the end of the latest menstruation period.

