The main analytical approach in Section 7.2.2 will be applied for this analysis.

In addition, sensitivity analysis for primary endpoint defined in section 7.2.3 will be applied for this analysis as well.

7.3.2 CFB in NMPP Measured by NRS at Week 12 and Week 24

The Baseline, Week 12 and Week 24 measurements will follow the definitions in sections of 7.2.1 and 7.3.1 for the time window, respectively.

The mean CFB and %CFB in NMPP at Week 12 and Week 24 will be summarized for each treatment group with point estimates (least square mean [LSM]), the associated standard errors [SEs]) and 95% CIs. Estimated treatment differences (compared for each HMI-115 treatment group against the placebo group) along with corresponding 95% CIs will be presented using the ANCOVA model with treatment group, region as the fixed effects and baseline NMPP as a continuous covariate.

The main analytical approach in Section 7.2.2 will be applied for this analysis.

In addition, sensitivity analysis for primary endpoint defined in section 7.2.3 will be applied for this secondary endpoint as well.

NMPP measured by NRS will be summarized by treatment and visit using observed values.

A by-subject listing will be presented for NMPP.

7.3.3 CFB in DYSP Measured by NRS at Week 12 and Week 24

For DYSP Measured by NRS, the Week 12 and Week 24 measurements will follow the definitions in sections of 7.2.1 and 7.3.1 for the time window, respectively.

The main analytical approach in Section 7.2.2 will be applied for this analysis.

In addition, sensitivity analysis for primary endpoint defined in section 7.2.3 will be applied for this secondary endpoint as well.

The mean CFB and %CFB in DYSP measured by NRS will be summarized by treatment and visit using observed values.

A by-subject listing will be presented for DYSP.

7.3.4 CFB in the Monthly (every menstruation cycle) Mean Endometriosis Daily Impact Pain Scale for DYS, NMPP and DYSP at Week 12 and Week 24

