Endometriosis Daily Impact Pain Scale will be used to record the mean change every month from Baseline to Week 12 measurement and Week 24 measurement. For DYS, NMPP and DYSP, responses of "None," "Mild," "Moderate," and "Severe" will be assigned a score of 0, 1, 2, and 3, respectively. For DYSP, the choice of "Not Applicable" applies to subjects not sexually active for reasons other than endometriosis pain. Responses of "Not Applicable" for the assessment of DYSP will be treated as missing values and will not be included in the summaries/analyses.

The average pain scores for DYS, NMPP and DYSP for Week 12 and Week 24 will follow the definitions in sections of 7.2.1 and 7.3.1 for the time window.

The main analytical approach in Section 7.2.2 will be applied for this analysis.

In addition, sensitivity analysis for primary endpoint defined in section 7.2.3 will be applied for this secondary endpoint as well.

Endometriosis Daily Impact Pain Scale for DYS, NMPP and DYSP will be listed.

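### The DYSP endpoints are imputed and reported for the whole PAS, although it can include women with no applicable DYSP rating or a DYSP baseline of 0

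*SAP*

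**What the plan says.** **Eligibility (Protocol 5.1, 10.4, 1.3).** Inclusion criterion 3 asks for a CPSSS "total score of ≥ 6 at screening with a score of at least 2 for DYS and at least 2 for NMPP". Criterion 4 asks for baseline diary "pain for DYS and NMPP, with NRS score of at least 4". Neither sets a minimum for DYSP. The contraception appendix lists "Is heterosexually abstinent" as one way to qualify, and the cytology footnote to the schedule of activities adds "Virgins may be exempted per the investigator's discretion".

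**Analysis set (SAP 3.3, 7.1).** The PAS is the FAS restricted to surgical diagnosis. It is the set for all efficacy analyses and carries no condition on sexual activity or baseline DYSP.

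**DYSP NRS (SAP 7.3, 7.3.3).** The row "Change of DYSP measured NRS from Baseline to Week 12 and 24" is assigned the primary endpoint's ANCOVA and multiple imputation. Section 7.3.3 repeats that 7.2.2 applies, then adds a separate descriptive summary: "The mean CFB and %CFB in DYSP measured by NRS will be summarized by treatment and visit using observed values". It has no rule for Not Applicable.

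**DYSP impact scale (SAP 7.3.4).** Not Applicable responses "will be treated as missing values and will not be included in the summaries/analyses". The same section then applies 7.2.2.

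**Percent change (SAP 7.2.5).** "Percentage change from Baseline = (the mean of Visit - the mean of Baseline) / the mean of Baseline)*100", with no rule for a baseline of 0.

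**The concern.** The DYSP analyses reuse the dysmenorrhea method, but dyspareunia differs in two ways. A woman may have nothing to rate, and entry does not require her to have any. A missing DYSP score can then mean that no such pain could occur, which is different from a missed diary or a withdrawal. The imputation rule makes no distinction.

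At stake is what a named secondary endpoint describes. A whole-PAS DYSP effect with a whole-PAS sample size would rest partly on women who contributed no DYSP data. Change and percent change would cover different women. Two programmers could also resolve 7.3.4 differently and obtain different tables.

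**Working it through.** **1. Can such women be in the PAS?** Each CPSSS component scores 0 to 3. DYS 3 + NMPP 3 = 6 meets the total with DYSP at 0 or Not Applicable. Criterion 4, the contraception rule and the PAS definition add no DYSP condition. So yes.

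**2. A woman with no applicable rating in the baseline cycle.** SAP 7.2.1 averages daily scores over days with data. With no such days the baseline mean does not exist, so change (visit minus baseline) is missing at every visit, whatever she reports later. Section 7.2.2 imputes any missing mean change, and its PROC MI variable list is treatment, region, baseline, Week 6 change and Week 12 change. Reused for DYSP, the last three are all missing for her. Her baseline and changes are drawn from treatment and region alone.

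**3. A woman with a DYSP baseline of 0.** Change = visit − 0, which cannot be negative. Percent change = (visit − 0)/0, which is undefined. Criterion 4 makes this unlikely for DYS and NMPP; nothing does so for DYSP.

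**4. SAP 7.3.4 set against 7.2.2.** At the level of the day the two fit: a Not Applicable day is left out of the average. They collide when every day in a cycle is Not Applicable. One sentence keeps those responses out of the analyses; the next sends the resulting missing mean to imputation. SAP 9.5 uses the same Not Applicable sentence for the CPSSS, but only with descriptive summaries, where no collision arises.

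**5. Size.** The plan has no DYSP power figure, so its DYS figures serve as a yardstick. By noncentral t, two-sided 0.05:

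- Within group, 1 point, SD 2.0, n = 34 (SAP 1.4): power 0.808.
- Between groups, 1.4 points, SD 2.0 (Protocol 9.2), n = 34: power 0.812.
- At n = 38 these are 0.851 and 0.853, so the stated 80% belongs to 34.

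The documents give no share of women without applicable DYSP, so the shares f below are assumptions. Imputed throughout = 34f; with data = 34(1 − f).

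| Assumed f | Imputed per arm | With DYSP data per arm | Power for 1.4 points | Difference detectable at 80% |
|---|---|---|---|---|
| 0% | 0 | 34 | 81% | 1.38 |
| 10% | 3.4 | 30.6 | 77% | 1.46 |
| 20% | 6.8 | 27.2 | 72% | 1.55 |
| 30% | 10.2 | 23.8 | 66% | 1.66 |
| 40% | 13.6 | 20.4 | 59% | 1.80 |

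For zero baselines, suppose a share g shows no change and the effect in the others is 1.4. The whole-set difference is 1.4(1 − g): 1.26, 1.12, 0.98 and 0.84 for g = 10%, 20%, 30% and 40%. At n = 34, holding SD at 2.0, power for the first three is 73%, 62% and 51%.

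**6. Does the imputation bias the estimate?** A simplified simulation used two arms of 34, a true difference of −1.4, 25 imputations and 300 runs, with women lacking all DYSP data chosen without regard to outcome. With 30% missing, imputation gave a mean of −1.35 (SD 0.58) and leaving the women out gave −1.35 (SD 0.57). At 10%, 20% and 40% the two also agreed closely. The imputed women added no information and, in this setting, no bias.

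**The case against.** Several objections stand.

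- **Bias.** A reader might infer that invented scores distort the treatment effect. The documents do not show this, and step 6 found no bias when missingness is unrelated to outcome.
- **Two analyses.** The quoted 7.3.3 sentence concerns observed values and imputes nothing. It carries the percent-change problem; the imputation comes from the separate instruction to apply 7.2.2.
- **Hidden exclusions.** A reader might say that percent change silently drops women. SAP 2.1 requires n in every continuous summary, and 7.3.3 provides a subject listing, so the difference would be visible though unexplained.
- **Self-contradiction.** Calling 7.3.4 flatly contradictory goes too far. The conflict is confined to women whose ratings in a cycle are all Not Applicable.
- **Dilution.** A smaller whole-set difference is an error only if the target is women with dyspareunia. The declared population is broader, and women with baseline 0 can worsen. The dilution figures also borrow a DYS effect.
- **No intercourse is not always inapplicable.** On the impact scale (Protocol 8.1.4), avoiding intercourse on account of pain scores 3. A blanket rule never to impute when there was no intercourse could drop badly affected women, and would exclude randomized women on post-baseline behaviour.
- **The NRS form is not reproduced.** A woman without intercourse may leave the item blank (imputed) or enter 0 (zero baseline). Those are alternatives for the same rating and should not both be counted.

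These narrow the point without removing it. On any reading, the SAP does not say what happens to a woman with no applicable rating in a cycle or with a baseline of 0, and the rule as written imputes the first.

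**Conclusion.** The point holds as a defect in how the DYSP endpoints are specified. Followed literally, SAP 7.2.2 gives imputed baselines and changes to women with no applicable baseline rating and reports them within a whole-PAS effect. Section 7.3.4 conflicts with that for women whose ratings are all Not Applicable, 7.3.3 has no such rule for the NRS, and percent change is undefined at a baseline of 0.

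The size cannot be computed from the documents. At an assumed 10% to 30%, about 3 to 10 of 34 women per arm would be imputed throughout. Information for a 1.4-point difference would be that of 31 to 24 women per arm (power 77% to 66%, against 81% at 34). This borrows the DYS effect and SD, and the PAS itself may be smaller than 34 per arm. Eligibility is read from Protocol 6.0; the SAP cites Protocol 6.1, which is not among the documents.

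Two stronger conclusions might be drawn and are not supported: that the imputation biases the DYSP comparison, and that the trial's main result is compromised. The primary DYS analysis is unaffected. The correction is still worth making, because a named secondary endpoint should not rest on scores for pain that could not be rated.

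**What to change.** Amend SAP 7.3.3 and 7.3.4:

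1. Define a DYSP-evaluable set from pre-dose data only: PAS subjects with at least one applicable DYSP rating in the baseline cycle. On the impact scale, count avoidance because of pain (score 3) as applicable. For the NRS, state how a day without intercourse is recorded and classed.
2. Run the DYSP change-from-baseline ANCOVA and multiple imputation in that set. Do not impute baseline or change for women outside it.
3. Keep set members who have no applicable rating after baseline. Handle them by the stated imputation, with a sensitivity analysis, so that nobody is dropped on post-randomization behaviour.
4. Compute percent change only where the baseline mean is above 0, and add a supplementary change-from-baseline analysis in that same subset.
5. Report by arm how many women fall outside each set.

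The cost is a few sentences, two pre-dose flags and a smaller n for DYSP. Membership depends on pre-dose data only, so the comparison between arms remains a randomized one.
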